3.6 Concomitant Medications, Treatments, and Procedures

Investigators may prescribe concomitant medications or treatments deemed necessary to provide supportive care except for prohibited medications (see Section 3.6.1) during treatment with SL-172154. Best supportive care should be provided when necessary for all subjects including antibiotics, bisphosphonates, receptor activator of nuclear factor kappa B ligand (RANKL) inhibitors, nutritional support, correction of metabolic disorders, optimal symptom control, and pain management including palliative radiotherapy after consultation with the Sponsor Medical Monitor.

Use of inhaled, topical, intranasal corticosteroids or local steroid injections (e.g., intra-articular injection) is permitted. Temporary use of corticosteroids (e.g., prior to computed tomography [CT] to prevent contrast allergies) is acceptable after consultation with the Sponsor Medical Monitor.

Aspirin is permitted at doses \leq 100 mg once daily. Chronic use of analgesic and/or anti-pyretic agents with no or low bleeding risk (for example, paracetamol/acetaminophen, metamizole, dipyrone, or propyphenazone) is recommended.

3.6.1 Prohibited Medications/Treatments

Subjects must be instructed not to take any medications, including over-the-counter products without first consulting with the investigator. The following medications are prohibited during study treatment with SL-172154:

- Any investigational anti-cancer therapy not described in this protocol
- Any concurrent chemotherapy, radiotherapy (except palliative radiotherapy after consultation with the Sponsor Medical Monitor), hormonal therapy, immunotherapy, or biologic therapy for cancer treatment
- Immunosuppressive medications for primary prophylaxis against injection-related reactions are not permitted. Subjects who require immunosuppressive medications (e.g., corticosteroids) for management of irAEs or injection-related reactions should be managed per Toxicity Management Guidelines in Section 3.7.
- Live attenuated vaccines during the study through 30 days after the last intratumoral dose of SL-172154
- Antiplatelet therapy (for example, clopidogrel, ticlopidine, dipyridamole, and anagrelide or $>$ 100 mg acetylsalicylic acid).
- Full dose anticoagulation therapy (for example, warfarin, heparin, low molecular weight heparin, direct oral anticoagulants). Low dose anticoagulant therapy for thromboprophylaxis is permitted.

- Local anesthetic administered prior to ITI of SL-172154 is not permitted due to the low pH of local anesthetic and the potential impact on the function of the drug product. Local anesthetic use is permitted prior to biopsy of a non-injected lesion.

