Target lesions: When more than one measurable tumor lesion is present at baseline all lesions up to a maximum of 10 lesions in total, representative of all involved organs, should be identified as target lesions and recorded and measured at baseline. Target lesion selection will not be capped at a maximum of 2 lesions per organ. Target lesions should be selected on the basis of their size (lesions with the longest diameter), be representative of all involved organs, but in addition should be those that lend themselves to reproducible repeated measurements. It may be the case that, on occasion, the largest lesion does not lend itself to reproducible measurement in which circumstance the next largest lesion which can be measured reproducibly should be selected. A sum of the diameters (longest for non-nodal lesions, short axis for nodal lesions) for all target lesions will be calculated and reported as the baseline sum diameters. If lymph nodes are to be included in the sum, then only the short axis is added into the sum. At baseline, the sum of the target lesions

(longest diameter of tumor lesions plus short axis of lymph nodes: overall maximum of 10) is to be recorded.

After baseline, a value should be provided on the eCRF for all identified target lesions for each assessment, even if very small. If extremely small and faint lesions cannot be accurately measured but are deemed to be present, a default value of 5 mm may be used. If lesions are too small to measure and indeed are believed to be absent, a default value of 0 mm may be used. The baseline sum diameters will be used as reference to further characterize any objective tumor regression in the measurable dimension of the disease.

Non-target lesions: All non-measurable lesions (or sites of disease) plus any measurable lesions over and above those listed as target lesions are considered **non-target lesions** and should also be recorded at baseline. Measurements of these lesions are not required, but the presence, absence, or in rare cases unequivocal progression of each should be noted throughout follow-up.

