6.9 Concomitant Procedures

Concomitant procedures include cancer-related or treatment-related procedures or palliative radiotherapy that is administered while on study therapy. Concomitant procedures along with start/end date and indication for the procedure will be presented in a data listing.

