7.1 Objective Response Rate

The ORR is defined as the proportion of subjects whose best overall response is a confirmed CR or confirmed PR based on investigator assessment according to RECIST 1.1. The ORR will be estimated with a 95% CI using the exact probability method. The number and percent of subjects with the best overall response of CR, PR, SD, PD and not evaluable (NE) will be summarized. Summary of objective response will be provided for the All Treated population and Response Evaluable population.

The best overall response based on RECIST 1.1 is defined as the best overall response among all post-baseline timepoint assessments until the first PD per RECIST 1.1 or start of new anti-cancer therapy, whichever is earlier. For subjects who have not met the criteria for PD per RECIST 1.1

or have not started a new anti-cancer therapy, the best overall response is defined as the best overall response among all post-baseline timepoint assessments.

Based on the investigator assessment of overall response per RECIST 1.1 at post-baseline assessments, the best overall response will be determined programmatically as the following and

Table 3:

- CR > PR > SD > PD > NE
- CR = at least two determinations of CR with at least 4 weeks apart before progression.
- PR = at least two determinations of PR or better with at least 4 weeks apart before progression (and not qualifying for CR).
- SD = at least one SD or better \geq 35 days after the first dose and before progression (and not qualifying for a CR or PR). The minimum interval from the first dose date for the best response of SD is 6 weeks minus 7 days to allow for visit windows of \pm 7 days (35 days).
- If the minimum interval for SD is not met, the best response will depend on the subsequent assessments. See table 3 for details.
- PD is considered the best overall response when PD is documented and a best overall response of CR, PR, or SD could not be established before documentation of PD. Clinical progression will not be considered as documented disease progression in the determination of the best overall response.
- NE is considered the best overall response when PD has not been documented and a best response of CR, PR or SD could not be established.

Table 3. Best overall response when confirmation of CR and PR required.

Overall response First time point	Overall response Subsequent time point	BEST overall response
CR	CR	CR
CR	PR	SD, PD or PR ^a

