CR	SD	SD provided minimum criteria for SD duration met, otherwise, PD
CR	PD	SD provided minimum criteria for SD duration met, otherwise, PD
CR	NE	SD provided minimum criteria for SD duration met, otherwise, NE
PR	CR	PR
PR	PR	PR
PR	SD	SD, provided minimum criteria for SD duration met, otherwise, PD
PR	PD	SD provided minimum criteria for SD duration met, otherwise, PD
PR	NE	SD provided minimum criteria for SD duration met, otherwise, NE

Overall response First time point	Overall response Subsequent time point	BEST overall response
NE	NE	NE

The best percent change from baseline in target lesion sum of diameters is defined as the largest reduction or smallest increase (in the case where a reduction does not occur) from baseline observed over all post-baseline disease assessments and will be presented using a waterfall plot.

Target lesion, non-target lesion, new lesion and response assessments will be presented in data listings. The percent change from baseline/nadir in target lesion sum of diameters will be kept 2 decimal places (xx.xx%) in the data listing and rounding is not required.

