7.5 Change from Baseline for Injected and Non-injected Lesions

Change from baseline diameter for each individual injected and non-injected lesion will be provided in a data listing. The best percent change from baseline for each individual injected and non-injected lesion will be presented using a waterfall plot.

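### Shrinkage of a lesion given permitted palliative radiotherapy would enter both waterfall plots as drug or bystander effect, and its handling in ORR is left undefined

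*Protocol*

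**What the plan says.** Protocol 3.6 groups this treatment with supportive care, naming "pain management including palliative radiotherapy after consultation with the Sponsor Medical Monitor". Protocol 3.6.1 repeats the allowance as an exception within the prohibited list: "radiotherapy (except palliative radiotherapy after consultation with the Sponsor Medical Monitor". Neither section spares target, injected or non-injected lesions.

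SAP 6.9 classifies it: "Concomitant procedures include cancer-related or treatment-related procedures or palliative radiotherapy that is administered while on study therapy". The only planned output is a listing: "Concomitant procedures along with start/end date and indication for the procedure will be presented in a data listing". The irradiated site is not among the listed fields.

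Three response outputs are relevant:

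- Best overall response (SAP 7.1) is taken over assessments "until the first PD per RECIST 1.1 or start of new anti-cancer therapy, whichever is earlier". The SAP does not define new anti-cancer therapy.
- Best percent change in the target-lesion sum (SAP 7.1) is the best value "observed over all post-baseline disease assessments and will be presented using a waterfall plot".
- For individual lesions (SAP 7.5): "The best percent change from baseline for each individual injected and non-injected lesion will be presented using a waterfall plot". No cut-off or exclusion is given.

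Protocol 16.5.1 requires that, after baseline, "a value should be provided on the eCRF for all identified target lesions for each assessment, even if very small". The same appendix calls previously irradiated lesions non-measurable unless they have since progressed. That text belongs to the definition of measurable disease and gives no instruction for a target lesion irradiated after baseline.

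**The concern.** A lesion irradiated on study can shrink because of the radiation. If it keeps being measured and nothing removes it from the analysis, the shrinkage is read as an effect of SL-172154. If the lesion was not injected, it looks like a bystander response, which Protocol 8.1.1 sets out to detect by splitting lesions on injected status.

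Lesion change by injected status is a stated secondary outcome, and clinical activity is one of the inputs to the RP2D choice. Protocol 6.8.4 directs injection towards larger and symptomatic lesions. Larger lesions carry more of the target sum, and symptomatic ones are plausible candidates for palliation. Protocol 6.8.1 lets an escalation subject enter with a single target lesion, so one irradiated lesion can be the whole sum.

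**Working it through.** **1. Where each output stops.**

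| Output | Stated end of window | Does palliative radiotherapy stop it? |
|---|---|---|
| Best overall response (SAP 7.1) | First PD or new anti-cancer therapy | Unclear: term undefined |
| Target-sum waterfall (SAP 7.1, Figure 14.2.2) | None: all post-baseline assessments | No |
| Per-lesion waterfall (SAP 7.5, Figure 14.2.3) | None stated | No |

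Neither waterfall stops at PD. Protocol 8.2 permits treatment beyond progression, so a lesion irradiated after PD can still feed both plots.

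**2. Effect on the plots (assumed lesion sizes).** Take two target lesions of 40 and 30 mm. The 40 mm lesion is irradiated and falls to 15 mm; the other does not change.

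- Target sum: (45 − 70)/70 = −35.7%
- Irradiated lesion: (15 − 40)/40 = −62.5%
- Unirradiated lesion: (30 − 30)/30 = 0%

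Both plots would show a substantial reduction, although the lesion that received no radiation did not change.

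**3. Shrinkage that meets the PR threshold by itself.** Protocol 16.5.2 sets PR at a 30% fall in the sum. If the irradiated lesion holds a share f of the baseline sum and the other lesions are unchanged, it must shrink by 0.30/f.

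| Share f | Shrinkage needed |
|---|---|
| 40% | 75% |
| 50% | 60% |
| 60% | 50% |
| 100% | 30% |

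A response would still need confirmation, and the investigator would still have to record it as one.

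**4. Effect on ORR if one such case were counted.** The planned denominator reproduces: 4 dose levels × 3 subjects + 6 = 18. SAP 7.1 specifies an exact 95% interval. With no responders, its upper limit is 1 − 0.025^(1/n); for n = 18 that is 18.5%. The other limits are Clopper-Pearson.

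| n | No responder | One responder |
|---|---|---|
| 18 (planned total) | 0% (0 to 18.5) | 5.6% (0.1 to 27.3) |
| 6 (goal at potential RP2D) | 0% (0 to 45.9) | 16.7% (0.4 to 64.1) |
| 3 (one cohort) | 0% (0 to 70.8) | 33.3% (0.8 to 90.6) |

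**5. How often it could arise.** The documents give no rate. If a proportion p of subjects is irradiated on study, the chance that at least one of 18 is affected is 1 − (1 − p)^18: 30% at p = 2%, 60% at 5%, 85% at 10% and 98% at 20%. These are chances of any on-study radiotherapy, not of a measured lesion being irradiated or of a false response.

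**The case against.** A reader might infer that the plan, followed as written, counts radiation shrinkage as an objective response. The documents do not go that far, for three reasons.

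- Best overall response is derived from the investigator's timepoint assessments, not recomputed from diameters. NE is an available category, so nothing obliges an investigator to record PR for an irradiated lesion.
- Whether palliative radiotherapy closes the response window is open. Protocol 3.6 and SAP 6.9 treat it as supportive care and a concomitant procedure. In the other direction, the washout table in Protocol 4.2 lists radiation under anti-cancer therapy while exempting palliative intent, and Protocol 3.6.1 names it as an exception among cancer treatments.
- The appendix text on previously irradiated lesions gives an investigator some basis for not crediting one, although it does not state a post-baseline rule.

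The case for low weight also has force. Eligible subjects are described as not amenable to further radiation, and each use needs consultation with the Medical Monitor. If radiotherapy follows documented PD, best overall response is already fixed. ORR is secondary and descriptive, with no hypothesis or threshold, and RP2D selection rests on the totality of data. The ORR intervals for zero and one responder overlap heavily. In a trial this small, a reader could compare the procedure dates with the lesion and response listings.

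These points narrow the ORR concern and lower the priority. They do not answer the two plots. Consultation governs permission and states no analysis consequence, and the listing does not identify the irradiated lesion.

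**Conclusion.** The concern holds for the two waterfall plots. As specified, both would show shrinkage of an irradiated lesion as SL-172154 or bystander effect. For ORR the plan is ambiguous, not demonstrably wrong: it neither says that palliative radiotherapy ends the response window nor how to assess a target lesion irradiated after baseline.

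The size is illustrative. It rests on assumed lesion sizes, an unknown radiotherapy rate and the planned 18 subjects. SAP 1 records that enrollment was discontinued early, as of 24 February 2022, so the actual number may be lower and each subject would then weigh more. If no measured lesion was irradiated, no result changes. Only secondary, descriptive outcomes are affected, so the priority is low to moderate. The point concerns analysis only, not whether radiotherapy should be permitted.

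**What to change.** Add one rule to SAP 7.1 and 7.5, applied from the start of radiotherapy to a given lesion:

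- **Per-lesion waterfall:** use only that lesion's assessments before radiotherapy.
- **Target-sum waterfall:** if the lesion is a target lesion, use only the subject's assessments before that date.
- **Best overall response:** treat an irradiated target lesion as not evaluable from that date, with timepoint response NE unless PD is shown elsewhere.

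Identify the irradiated lesion in the concomitant-procedure data, by site query where it was not collected. SAP 1 says analysis decisions precede Database Freeze, so the rule should be fixed before then rather than chosen after seeing the plots.

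The cost is a few NE or excluded assessments and possibly a few retrospective site queries, since the SAP was updated after enrollment had stopped. Ending the response window at radiotherapy would also resolve the ORR ambiguity, but alone it would leave both plots unchanged.

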3.6.2 Medications to be used with Caution

SL-172154 is a therapeutic protein that may induce the transient release of cytokines including IL-6 which in turn, may inhibit the activity of cytochrome P450 (CYP450) enzymes including CYP3A4 activity [Evers, 2013]. Although not tested clinically, a drug-drug interaction may occur with the coadministration of medications that are CYP450 substrates. Drugs metabolized by CYP450 enzymes may have reduced clearance or an increase in half-life or peak plasma concentration and should be used with caution. There may be an increased risk of side effects for drugs that are CYP450 substrates. Where possible, consider substitutions for these medicinal products if therapeutic effects cannot be monitored during ITI of SL-172154. A complete list of drugs that are CYP450 substrates including CYP3A4 substrates is available at: <https://drug-interactions.medicine.iu.edu/Main-Table.aspx> (Flockhart Table).

Chronic use of non-steroidal anti-inflammatory drugs (NSAIDs) with a high risk of bleeding (for example, indomethacin, ibuprofen, naproxen, or similar agents) is strongly discouraged unless at the discretion and responsibility of the investigator after careful assessment of the individual bleeding risk of the subject.

3.7 Toxicity Management Guidelines Dosing Delays/Dose Modifications

No dose reductions are permitted for SL-172154. The toxicity guidelines provided in this section represent general guidance for AEs that are considered by the investigator to be related to treatment with SL-172154. All AEs should be assessed using NCI-CTCAE v5.0 criteria. These guidelines are not meant to be prescriptive and investigators should always use clinical judgment in the determination of dosing. Investigators should always err on the side of caution if treatment-related toxicity is suspected. Subjects should be thoroughly evaluated to rule out any alternative etiology (e.g., disease progression, concomitant medications, and infections). In the absence of a clear alternative etiology, all events should be considered potentially immune related.

Please see Section [5.1.4 Monitoring Dose Administration](#) for further information on ITI of SL-172154. In this protocol, the term “injection-related reactions” maps to the analogous term of “infusion-related reaction” in CTCAE v5.

NOTE: Hereafter in this section and in subsequent sections, SL-172154 may be referred to as SL-172154 or as IP.

Differentiating between injection-related reactions that are due to either the common non-allergic hypersensitivity reactions [HSRs (e.g., CRS)] or the rarer allergic HSRs can be challenging due to overlapping clinical manifestations. There are no specific clinical features (including symptoms and timing of reaction) that can absolutely distinguish between these two entities. General guidance is provided below for injection-related reactions secondary to both allergic and non-allergic HSRs e.g., CRS. These guidelines are not meant to be prescriptive. Established institutional guidelines should be followed where appropriate. At the resolution of the event, the

entirety of the data including clinical symptoms, response to treatment and laboratory studies should be re-evaluated to determine the final etiology of the event. For purposes of standardized reporting, utilize terms based on best medical judgment of the AE/SAE and the definition found in NCI-CTCAE v5.0 for injection-related reaction, allergic reaction, anaphylaxis, and CRS.

Primary prophylaxis against injection-related reactions is not permitted to avoid obscuring a potential safety signal and to enable an assessment of whether pre-medications should be required for all subjects. However, as noted in the guidance below, secondary prophylaxis (i.e., prevention of injection-related reactions following an initial episode) is appropriate and permitted at the discretion of the investigator.

NOTE: In the event of a Grade ≥ 2 injection-related reaction, subjects will be observed on-site or hospitalized for close observation until resolution of symptoms as per Section [3.7.1](#).

3.7.1 Toxicity Management Guidelines

Adverse Event	General Guidance for Injection Site Reactions (ISR)						
Injection Site Reactions	
Subjects will be monitored closely throughout the study for the following symptoms at the injection sites: pain, tenderness, pruritis, warmth, cellulitis, rash, erythema, swelling, induration, fluctuance, and nodules (granulomas or cysts). Digital photographs will be documented by the study team for evaluation on all subjects who have an injection site reaction that are serious, Grade 2 or above or if persistent beyond 2 weeks. Dermatology will be consulted on all subjects who have an injection site reaction considered serious, Grade 3 or above, or if persistent beyond 30 days and others if the Investigator or Medical Monitor feels it is medically necessary.
						
Severity	
  
 Symptoms	Management	
   
 Grade 1	 
 Continue SL-172154 injection with close clinical follow-up. Symptomatic treatment and/or premedication of local injection site reactions with antihistamines (H1/H2 inhibitors), acetaminophen (or other low bleeding risk medications; Section 3.6) and opiates is acceptable. Antileukotrienes may also be considered as needed per discretion of the investigator. Due to their potential bleeding/immunosuppressive effects, the use of systemic NSAIDs and steroids within 24 hours of dosing SL-172154 should be avoided, if clinically feasible. Temporarily hold SL-172154 injection until AE has reverted to Grade 1 or baseline. Provide symptomatic treatment with acetaminophen as anti-pyretic, antihistamines, leukotriene inhibitors and/or opiates. 	
 
 Grade 2	 
 Provide premedication prior to subsequent injections per investigator/institutional guidelines. Due to their potential bleeding/immunosuppressive effects, the use of systemic NSAIDs and steroids within 24 hours of injection with SL-172154 should be avoided if clinically feasible. If SL-172154 injection is delayed such that 2 consecutive scheduled injections are missed to allow for resolution of ISR despite optimal medical management, then the subject should permanently discontinue SL-172154 injections. 	
  
	Symptoms	Management	Grade 1	
 Continue SL-172154 injection with close clinical follow-up. Symptomatic treatment and/or premedication of local injection site reactions with antihistamines (H1/H2 inhibitors), acetaminophen (or other low bleeding risk medications; Section 3.6) and opiates is acceptable. Antileukotrienes may also be considered as needed per discretion of the investigator. Due to their potential bleeding/immunosuppressive effects, the use of systemic NSAIDs and steroids within 24 hours of dosing SL-172154 should be avoided, if clinically feasible. Temporarily hold SL-172154 injection until AE has reverted to Grade 1 or baseline. Provide symptomatic treatment with acetaminophen as anti-pyretic, antihistamines, leukotriene inhibitors and/or opiates. 	Grade 2	
 Provide premedication prior to subsequent injections per investigator/institutional guidelines. Due to their potential bleeding/immunosuppressive effects, the use of systemic NSAIDs and steroids within 24 hours of injection with SL-172154 should be avoided if clinically feasible. If SL-172154 injection is delayed such that 2 consecutive scheduled injections are missed to allow for resolution of ISR despite optimal medical management, then the subject should permanently discontinue SL-172154 injections.
Symptoms	Management						
Grade 1	
 Continue SL-172154 injection with close clinical follow-up. Symptomatic treatment and/or premedication of local injection site reactions with antihistamines (H1/H2 inhibitors), acetaminophen (or other low bleeding risk medications; Section 3.6) and opiates is acceptable. Antileukotrienes may also be considered as needed per discretion of the investigator. Due to their potential bleeding/immunosuppressive effects, the use of systemic NSAIDs and steroids within 24 hours of dosing SL-172154 should be avoided, if clinically feasible. Temporarily hold SL-172154 injection until AE has reverted to Grade 1 or baseline. Provide symptomatic treatment with acetaminophen as anti-pyretic, antihistamines, leukotriene inhibitors and/or opiates. 						
Grade 2	
 Provide premedication prior to subsequent injections per investigator/institutional guidelines. Due to their potential bleeding/immunosuppressive effects, the use of systemic NSAIDs and steroids within 24 hours of injection with SL-172154 should be avoided if clinically feasible. If SL-172154 injection is delayed such that 2 consecutive scheduled injections are missed to allow for resolution of ISR despite optimal medical management, then the subject should permanently discontinue SL-172154 injections. 						

Injection site reaction (continued from previous page)	Severity (Symptoms)	Management
	Grade 3	
 • Hold SL-172154 injection until AE has reverted to Grade 1 or baseline. • Provide symptomatic treatment with acetaminophen as anti-pyretic, antihistamines, leukotriene inhibitors, steroids and/or opiates. • Obtain dermatology consultation. • If grade 3 AE persists for \geq 7 days, permanently discontinue SL-172154 injections. • Provide pre-medications (acetaminophen as anti-pyretic, antihistamines, leukotriene inhibitors, steroids and/or opiates) for subsequent injections per investigator/institutional guidelines. • If grade 3 symptoms recur with pre-medications, then SL-172154 injections should be permanently discontinued.
	Grade 4	
 • Permanently discontinue SL-172154 injections. • Obtain dermatology consultation. • Treat urgently with non-operative and operative interventions as clinically indicated.

Adverse Event	General Guidance for Injection-related Reactions [Rosello, 2017; Porter, 2018]
Severity (Symptoms)	Management
Injection-Related or Hypersensitivity Reactions	
In this protocol, the term “injection-related reactions” maps to the analogous term of “infusion-related reaction” in CTCAE v5. Acute reactions to the administration of biologic agents are not uncommon. Reactions are either allergic reactions to foreign proteins or non-immune reactions. The term HSR is used to describe objectively reproducible signs or symptoms initiated by exposure to a defined stimulus at dose tolerated by a normal person. Allergy is an HSR initiated by specific immunological mechanisms. Anaphylaxis is a severe, life threatening HSR. CRS consists of a non-allergic, cytokine mediated HSR. Differentiation between the common non-allergic HSR reactions and the rarer allergic HSR reactions can be challenging due to overlapping clinical manifestations. Fever, chills, rigors, headache, arthralgias, back pain, abdominal pain, nausea, vomiting, diarrhea, dyspnea, flushing, pruritus, and changes in heart rate and blood pressure are common manifestations of acute infusion reactions. Proinflammatory cytokines such as TNF-α and IL-6 may play a role in these reactions. Symptoms more suggestive of allergic HSR include generalized pruritus, urticaria, wheezing, frequent coughing, and anaphylactic symptoms. Subjects must be monitored for signs and symptoms of injection-related reactions with prompt institution of treatment. Subjects should be notified that symptoms may occur during the first injection and for up to several hours afterwards or with subsequent injections. Instruct subjects to contact their physician if symptoms or signs of an injection-related reaction occur.

Grade 1	
Injection(s) interruption not indicated.Monitor subjects with close observation in an outpatient or inpatient setting for a minimum of 12 hours or until recovery from symptomsConsider pre-medication (antipyretics, histamine (H1 and H2 antihistamines, leukotriene inhibitors, corticosteroids) for subsequent injections per investigator/institutional guidelines
Grade 2	
Consider interrupting SL-172154 injection(s).Begin IV infusion of normal saline and treat with antipyretics, histamine 1 and 2 (H1 and H2) antihistamines, and leukotriene inhibitor. Corticosteroids and/or bronchodilator therapy may also be administered as appropriate.If symptoms resolve with treatment, SL-172154 injection(s) may be completed. If symptoms recur or do not resolve to baseline, then no further SL-172154 injection(s) will be administered at this visit.Monitor subjects with close observation in an outpatient or inpatient setting for a minimum of 12 hours or until recovery from symptoms. Consider admission to hospital.The following prophylactic pre-medications are recommended for future injections: antipyretics, antihistamines with/without corticosteroids per institutional guidelines

Injection-related or Hypersensitivity reactions (continued from previous page)	Severity (Symptoms)	Management
Grade 3		
 • Immediately discontinue injection(s) of SL-172154 • Begin IV infusion of normal saline and treat with epinephrine, bronchodilators, diphenhydramine, ranitidine, corticosteroids, oxygen, fluids, vasopressors, etc. as indicate and per institutional guidelines. Epinephrine is the drug of choice in an anaphylactic reaction and its administration should not be delayed. • Monitor subjects with close observation in an outpatient or inpatient setting for a minimum of 12 hours or until recovery from symptoms. Strongly consider admission to hospital. • Rechallenge should not be attempted in cases of true anaphylaxis. In other cases, once subject has completely recovered, carefully consider if it is safe for the subject to receive SL-172154 injection at the next scheduled dose with pre-medication (e.g., corticosteroids, antihistamines, antipyretics). The next two subsequent injections of SL-172154 (after a grade 3 event of injection-related reaction) must be administered in an inpatient or outpatient setting with prolonged observation for a minimum of 12 hours after the completion of the injection. If symptoms recur, permanently discontinue SL-172154. • Permanently discontinue SL-172154 injection(s). • Admit to hospital for close observation until resolution of symptoms
Grade 4		
 • Manage severe injection-related reactions per institutional standards (e.g., epinephrine, diphenhydramine, ranitidine, corticosteroids, bronchodilators, oxygen, fluids etc.). Epinephrine is the drug of choice in an anaphylactic reaction and its administration should not be delayed

General Guidance for Cytokine Release Syndrome (CRS) [Rosello, 2017; Porter, 2018]		
Adverse Event	Severity (symptoms)	Management
Cytokine-release Syndrome	CRS is a non-antigen specific, systemic inflammatory response that occurs as result of high-level immune activation with concomitant elevations of cytokines (e.g., IL-6, IL-10, TNF- α , IL-2, IFN γ). Clinical features of the syndrome include (but are not confined to) fever, flu-like symptoms, rash, nausea, vomiting, diarrhea, hypotension, tachypnea, transaminitis, hypofibrinogenemia, elevation in D-dimer, hyperbilirubinemia, azotemia, neurologic manifestations. The syndrome can progress to life-threatening capillary leak, hypoxic respiratory failure, vasodilatory shock and end-organ dysfunction. NOTE: CRS may have a similar presentation to a type 1 HSR and may be clinically indistinguishable.	
 Injection(s) interruption is not indicated. Monitor subjects with close observation in an outpatient or inpatient setting for a minimum of 12 hours or until recovery from symptoms. Maintain IV access and provide symptomatic treatment with antipyretics, antiemetics, analgesics, histamine 1/histamine 2 (H1/H2) antagonists as needed; monitor fluid balance; assess for infection. Regularly evaluate for signs of further deterioration For subsequent injection(s), consider pre-medication (e.g., antipyretics, antihistamines) per institutional guidelines
Grade 1		
 Interrupt SL-172154 injection(s). Start IV infusion with normal saline. Administer oxygen if needed. Treat with antipyretics, H1/H2 antagonists (diphenhydramine 50 mg IV plus ranitidine 50 mg IV), and/or methylprednisolone 1-2 mg/kg or equivalent dose of corticosteroid every 6 hours and manage per institutional guidelines. Closely monitor cardiac and other organ functions. Monitor subjects with close observation in an outpatient or inpatient setting for a minimum of 12 hours or until recovery from symptoms. Consider admission to hospital for management of symptoms, organ dysfunction or administration of therapy
Grade 2		
 The next two subsequent injections of SL-172154 (after an event of grade 2 CRS) must be administered in an inpatient or outpatient setting with prolonged observation for a minimum of 12 hours after the completion of the injection. For subsequent injections, pre-medicate with dexamethasone 20 mg, antipyretics, H1/H2 antihistamines, and manage per institutional guidelines. Subjects with extensive comorbidities or those of older age should be treated as for Grade 3. Subjects with worsening symptoms should be treated as for Grade 3

Adverse Event	Severity (Symptoms)	Management

Cytokine-release Syndrome (continued from previous page)
 
Grade 3 or 4
	
 Interrupt SL-172154 injection(s). Hospitalization required for management of symptoms related to organ dysfunction: admit to the hospital and potentially the intensive care unit or equivalent for close monitoring and management Treat hypotension with IV fluid for blood pressure support and/or pressors. Administer oxygen for treatment of hypoxia. Cryoprecipitate or fresh frozen plasma may be required for coagulopathy. Manage per institutional guidelines. Manage severe injection-related reactions and CRS per institutional standards (e.g., epinephrine, diphenhydramine, ranitidine, corticosteroids, bronchodilators, oxygen, fluids etc.). Epinephrine is the drug of choice in an anaphylactic reaction and its administration should not be delayed Administer tocilizumab at a dose of 8 mg/kg. If clinical improvement does not occur within 24 hours, administer a second dose of tocilizumab. Second-line therapies: 
 Methylprednisolone 2 mg/kg/day IV tapered over several days. For subjects with severe neurologic symptoms, consider using dexamethasone due to more efficient penetration of the blood-brain barrier. anti-TNF-α mAbs (infliximab) or soluble TNF-α receptor (etanercept), or IL-1R-based inhibitors (anakinra). For Grade 3 CRS, may consider rechallenge after consultation with medical monitor. If rechallenge is given: 
 The next two subsequent injections of SL-172154 (after an event of grade 3 CRS) must be administered in an inpatient or outpatient setting with prolonged observation for a minimum of 12 hours after the completion of the injection. After a Grade 3 CRS event, subjects must be premedicated with dexamethasone 20 mg, antipyretics and H1/H2 antihistamines prior to the next injection of SL-172154. 
 If there is no evidence of CRS with the subsequent injection, premedication with high dose steroids may be omitted for subsequent injections. Any patient that experiences recurrence of Grade 3 CRS following re-treatment must be permanently discontinued from study treatment. For Grade 4 CRS, permanently discontinue SL-172154. 	

Adverse Event	General Guidance for Management of Immune-related Adverse Events (irAEs) [Haanen, 2017; Puzanov, 2017; Brahmmer, 2018]
	
Guidelines for management of irAEs across body systems are outlined in this section. These guidelines are not meant to be prescriptive. Established institutional guidelines should be followed where appropriate. Severity of irAE are categorized according to NCI CTCAEv5. Limitations of classification and grading by CTCAEv5 for specific irAEs may be encountered. Based on the severity of the irAE, SL-172154 may either be continued, held or permanently discontinued. Management relies heavily on corticosteroids and other immunomodulatory agents. Generally, the decision on IP and institution of immunosuppressive therapy (corticosteroid therapy) can be approached as noted below. However, treatment should be individualized depending on the subject's medical history, the nature and severity of the AE, co-morbidities, and ability to tolerate corticosteroids. When starting corticosteroid therapy, consider initiating proton pump inhibitors for gastrointestinal (GI) toxicity prophylaxis. Once toxicity has improved to \leq Grade 1 AE, start tapering corticosteroid therapy over a 4 to 6-week period. Add pneumocystis pneumonia prophylaxis (cotrimoxazole or inhaled pentamidine if cotrimoxazole allergy) if more than 3 weeks of immunosuppression expected (>30 mg prednisone or equivalent). Consider calcium & vitamin D supplementation as per local guidelines.

irAEs - General

Severity (Symptoms)	Management
Grade 1	
 SL-172154 injection is continued, and treatment with corticosteroids is usually not indicated SL-172154 injection may be continued. 
 Depending on the nature of the AE, corticosteroids may be indicated. Start with oral prednisone 0.5-1 mg/kg/day. SL-172154 is generally held during corticosteroid therapy and until irAE has resolved to \leq Grade 1 and corticosteroids have been tapered to \leq prednisone 10 mg/day (or equivalent) or discontinued. If IV therapy is required, use methylprednisolone 0.5 – 1 mg/kg/day. If no improvement in symptoms, the dose may be increased to 2 mg/kg/day. Hold SL-172154 injection.
Grade 2	
 Start prednisone 1-2 mg/kg/day (or equivalent dose of methylprednisolone). If no improvement, consider adding alternative immune suppressant therapy.
